## 7.2 Statistical Methods

The primary outcome is spontaneous preterm birth before 34 weeks of gestation. Secondary outcomes include gestational age at delivery, interval between diagnosis and delivery, birth weight, spontaneous preterm birth rates at less than 24, 28, 32 and 37 weeks gestation and spontaneous rupture of membranes at less than 34 weeks gestation. Secondary safety outcomes include admission to NICU, neonatal death, length of stay in the NICU until discharge home, composite adverse neonatal outcome that includes necrotizing enterocolitis (stage 3 or 4), intraventricular hemorrhage (grade 3 or 4), respiratory distress syndrome (grade 3 or 4), need of intubation and mechanical ventilation, retinopathy of prematurity requiring laser treatment (stage 3 or 4) and proven sepsis requiring treatment), and significant adverse maternal effects will include: intraoperative rupture of membranes, clinical or histological chorioamnionitis, postpartum hemorrhage, cervical tear and uterine rupture). Neonatal mortality prior to discharge home form the hospital.

Statistical analysis will be based on the intention-to-treat principle. Comparisons between the two groups will be made with the Mann-Whitney U test. Univariate comparisons of dichotomous data will be performed with Fishers exact test. The p values for all hypotheses will be two sided, and p values of less than 0.05 will be considered to be significant. The risk of spontaneous preterm birth before 34 weeks will be quantified by use of the relative ratio and 95% confidence interval. Multivariate analysis will be performed using logistic regression. The risk of spontaneous preterm birth from randomization until delivery will be assessed with Kaplan-Meier analysis, in which gestational age is the timescale, spontaneous delivery is the event, and elective deliveries are censored. SPPS software package (version 16.0) will be used for all statistical analyses.

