## 1.3 Risk/Benefits

The major risks of ultrasound indicated cerclage that have been reported in previous studies involving singleton pregnancies include intraoperative rupture of membranes (less than 1%), cervical laceration, cervical bleeding, chorioamnionitis (undiagnosed at the time of cerclage or acquired post cerclage placement), failure to place the cerclage and failure of the cerclage on prolonging pregnancy with possible pregnancy loss or delivery at a periviable gestational age around 23-25 weeks of gestation. Other risks are those associated with anesthesia during the surgical procedure: hypotension, allergy to medications, headache. To limit these risks, the anesthetic route is typically regional anesthesia. Later on during the course of pregnancy, other risks maybe present as preterm contractions with the cerclage in place may cause laceration of the cervix and bleeding in which case the cerclage needs to be removed.

Minor side effects include increased vaginal discharge, there is a theoretical disruption the vaginal flora associated with foreign object, and minimal discomfort at the time of cerclage removal.

The potential benefits include prolongation of pregnancy, decreased very preterm delivery (< 28 weeks), very low birth weight (<1500 grams) and decreased in composite morbidity for the newborn (respiratory distress syndrome, need of intubation and mechanical ventilation, intraventricular hemorrhage, necrotizing enterocolitis, sepsis and retinopathy of the preterm newborn) and length of admission in the neonatal intensive care unit. Decreased perinatal mortality. These potential benefits are based on results of previous retrospective cohorts available in twin pregnancies.

All of the investigators have received formal training on ultrasound indicated cerclage placement. The training and experience of the investigators will minimize the risks associated with cerclage placement.

Our protocol specifically states that the cervical cerclage will be removed if the patient goes into labor, has preterm premature rupture of membranes (PPROM), presents with active cervical bleeding, or if she remains asymptomatic and reaches 36 weeks of gestation.

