## Secondary safety endpoints:

- Admission to the NICU and length of stay if admitted
- Neonatal death before discharge from hospital
- Composite adverse neonatal outcome (includes any of the following: necrotizing enterocolitis (grade 3 or 4), Intraventricular hemorrhage (grade 3 or 4), respiratory distress syndrome (grade 3 or 4), need for intubation and mechanically assisted ventilation, retinopathy of the newborn requiring laser treatment (grade 3 or 4), and proven sepsis with positive culture).
- Clinical Chorioamnionitis
- Histological chorioamnionitis (It is standard of care to send placenta to pathology for multiple gestations).
- Significant adverse maternal effects including intraoperative rupture of membranes, bleeding, and cervical laceration (tear).

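### Intraoperative rupture of membranes falls under the between-arm Fisher rule, although unoperated controls cannot have it; risk per operation should be reported with an exact interval instead

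*Combined protocol and SAP*

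**What the plan says.** Section 3.3 lists, among the secondary safety endpoints, "Significant adverse maternal effects including intraoperative rupture of membranes, bleeding, and cervical laceration (tear"). Section 7.2 gives a slightly different list: "significant adverse maternal effects will include: intraoperative rupture of membranes, clinical or histological chorioamnionitis, postpartum hemorrhage, cervical tear and uterine rupture".

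The analysis rules in Section 7.2 are general:

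- Analysis set: "Statistical analysis will be based on the intention-to-treat principle".
- Test: "Univariate comparisons of dichotomous data will be performed with Fishers exact test".
- Significance: "The p values for all hypotheses will be two sided, and p values of less than 0.05 will be considered to be significant".

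The only effect estimate with a confidence interval in that section is for the primary outcome. It plans no summary by procedure received, no cerclage-arm-only summary and no interval for procedural harm.

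Section 1.3 supplies the one reference rate. The major risks of the procedure "include intraoperative rupture of membranes (less than 1%), cervical laceration, cervical bleeding" and further items. These are described as "reported in previous studies involving singleton pregnancies". The rate is attached to intraoperative rupture of membranes only.

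**The concern.** A woman who has no operation cannot have an intraoperative event. The null hypothesis of Fisher's test, equal risk in the two arms, is therefore not a meaningful question for intraoperative rupture of membranes. The test only asks whether the cerclage count is large enough to be distinguished from a zero that the design imposes. The useful questions are how high the risk is per operation in this population, and whether it is compatible with the singleton figure.

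The denominator is a second problem. Under intention to treat it is every woman allocated to cerclage. Some of them may never be operated on: Section 4.3 places insurance precertification between randomization and surgery, and Section 5.2 allows withdrawal after randomization. Conversely, an event in a control woman who crosses over to cerclage would count against expectant management.

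At stake is the trial's account of procedural risk. Section 1.1 says that no trial has evaluated cerclage specifically in twins at 15 mm or less, and Section 1.2 counts only 7 such women in the earlier pooled randomized data. A non-significant p-value would be a poor summary of what this trial learns about that risk.

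**Working it through.** **Inputs.** Section 7.1: 93 per arm before the loss allowance, 100 per arm after it. Section 7.2: Fisher's exact test, two-sided 0.05. Section 1.3: less than 1% for intraoperative rupture of membranes. Assumptions: no control woman has a cerclage, unless stated otherwise; the share of allocated women operated on is not given, so a range is shown.

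**1. The plan's own figure.** For 70% vs 50%, with pooled variance under the null:

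n = [1.960·√(2·0.6·0.4) + 0.842·√(0.7·0.3 + 0.5·0.5)]² / 0.20² = 93 per arm, 186 in total.

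This reproduces Section 7.1. It concerns the primary endpoint only; the documents state no power or precision for any safety outcome.

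**2. Fisher's test against zero.** With equal arms of size N and x events against 0, the two-sided p-value is 2·C(N,x)/C(2N,x). For x=5 and N=100:

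2 × (100·99·98·97·96)/(200·199·198·197·196) = 2 × 0.02969 = 0.059.

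| Events in cerclage arm (0 in control) | p, 100 per arm | p, 93 per arm |
|---|---|---|
| 4 | 0.121 | 0.121 |
| 5 | 0.059 | 0.059 |
| 6 | 0.029 | 0.029 |

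Six events are needed for p<0.05.

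**3. Exact interval for the same data.** The Clopper-Pearson limits are the 2.5% quantile of Beta(x, N−x+1) and the 97.5% quantile of Beta(x+1, N−x). For 5/100 they are 1.6% and 11.3%; for 5/93 they are 1.8% and 12.1%. If the true rate were 1%, the probability of 5 or more events in 100 would be 0.003. The data that Fisher's test calls not significant thus lie above the quoted reference.

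**4. If 5% is the true rate.** The chance of p<0.05 is P(X≥6) for X ~ Binomial(N, 0.05): 38.4% at N=100 and 32.1% at N=93. Not significant would therefore be reported in about 62% to 68% of such trials. Power near 80% needs a true rate of about 8% (82.0% at 100 per arm, 76.3% at 93).

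**5. Denominator (assumed range).** If 85 of 100 allocated women are operated on, 5 events are 5/85 = 5.9% per operation, but 5/100 = 5.0% by intention to treat. With a 5% rate per operation, the chance of reaching 6 events falls from 38.4% (100 operated on) to 29.5% (90), 25.2% (85) and 21.1% (80).

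**6. One crossover event (assumption).** 5/100 vs 1/100 gives p=0.21.

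**The case against.** - **Section 7.2 does not assign Fisher's test to this endpoint by name.** True. The application follows from a general rule to which the section makes no exception. Nothing forbids printing the counts, and a reader would see 5 against 0. But the plan commits to no denominator of operated women and no interval.

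- **Other safety provisions look at excess frequency.** Section 8.1 defines unanticipated surgical effects partly by degree of incidence. The list of other reportable events includes a side effect that is more frequent than expected. Section 8.2 requires adverse surgical effects to be recorded, Section 8.4 requires regular assessment of their number and type, and Section 8.4.1 sets a DSMB safety review at about 50% delivered. Detection of excess harm therefore does not rest on Fisher's test alone. None of these provisions, however, yields a final estimate with a denominator.

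- **Only one listed item is surgery-only.** This stands. A reader might infer that the whole maternal list is affected. It is not: chorioamnionitis, postpartum hemorrhage, cervical tear and uterine rupture can occur in either arm, and the randomized comparison suits them. Replacing their p-values with risk differences would be a preference, not a correction.

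- **The reference rate is an imprecise upper bound.** This also stands. It would be tempting to set the 38% beside the probability that the exact interval excludes 1%, as if two methods were competing. They answer different questions, one a difference from control and the other an excess over 1%.

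- **Stronger claims about importance are not supported.** A reader might infer that participants were given the figure of less than 1%. The consent pages are not among the documents, and Section 1.3 is protocol text. Nor would these be the first randomized data of any kind, given the 7 women in Section 1.2.

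**Conclusion.** The point holds for intraoperative rupture of membranes. Followed as written, Section 7.2 tests this harm against a structural zero, over a denominator that may include women never operated on, and gives no estimate of risk per operation.

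A reader might infer that a true rate five times the quoted bound would necessarily be reported as not significant. That is certain only for an observed count of five or fewer against zero. For a true 5% it is likely, not certain. These figures assume that every woman allocated to cerclage is operated on and that no control woman is. Departures from either assumption weaken the contrast further, but the documents give no rate for them, so the denominator effect is illustrative.

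Severity is low: one secondary safety item is affected, and the primary analysis and sample size are unchanged.

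**What to change.** In Section 7.2:

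1. Exempt from the between-arm test intraoperative rupture of membranes, and any bleeding or laceration recorded as occurring during the cerclage procedure.
2. For these events, report the count, the number of women in whom cerclage was attempted whatever their allocation, and the exact (Clopper-Pearson) 95% CI. Label the table as a non-randomized description. Women in whom placement was attempted but failed belong in the denominator.
3. Set the interval beside the singleton figure of less than 1% for intraoperative rupture of membranes only, since Section 1.3 gives no rate for the other events.
4. Keep the planned intention-to-treat comparison for maternal harms possible in both arms: chorioamnionitis, postpartum hemorrhage, cervical tear and uterine rupture.

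The cost is a few lines of SAP wording and one extra table. Its downside is that the table is not a randomized comparison and cannot be read as one. For bleeding and laceration, the record must show whether the event occurred during the procedure. No change to sample size, treatment or the primary analysis is needed.

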# Study Summary

Title	Cervical cerclage for preventing spontaneous
	preterm birth in twin pregnancies with
	transvaginal ultrasound cervical length ≤ 15mm:
	a study protocol for a randomized clinical trial
Short Title	Cerclage for Twins with short cervix
Methodology	Multi-center, open label, randomized trial
Study Duration	3 years for subject enrollment, and an additional
	6 months for analysis and manuscript
	preparation: 2017-2021
Study Center	Thomas Jefferson University
Objectives	The primary objective of this study is to
	determine if ultrasound indicated cerclage
	reduces the incidence of spontaneous preterm
	birth in asymptomatic women with twin
	gestations with transvaginal ultrasound cervical
	length ≤ 15mm before 24 weeks of gestation.
Number of Subjects	200
Diagnosis and Main Inclusion Criteria	Women, age older than 18, with a twin gestation
	and transvaginal ultrasound cervical length
	≤15mm between 16 to 23 6/7 weeks gestation
Study Product and Planned Use	Cervical cerclage
Reference therapy	Standard obstetrical care include daily vaginal
	progesterone 400mg from diagnosis of cervical
	length ≤25mm (usually 20 weeks) to 36 weeks
Statistical Methodology	Statistical analysis will be based on the intention-
	to-treat principle. The risk of spontaneous
	preterm birth before 34 weeks will be quantified
	by use of the odds ratio and 95% CI. Multivariate
	analysis will be performed using logistic
	regression.
	1

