## 3.2 Primary Study Endpoints

Spontaneous preterm delivery at less than 34 weeks gestation

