#### **7** Statistical Plan

## 7.1 Sample Size Determination

Calculation of sample size was based on a reduction in the incidence of spontaneous delivery before 34 weeks from 70% in the expectant management group to 50% in the cerclage group, with a power of 80%. To detect this difference at a significance level of 5%, we will need to enroll a total of 186 subjects with 93 subjects in each arm, plus 10% for loss of follow up. Total 200 subjects with 100 subjects in each arm

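### Primary p value (Fisher's exact test) and primary 95% interval (method unnamed; relative ratio in 7.2, odds ratio in the Study Summary) are not a matched pair: borderline results can conflict, and Fisher costs about 4 to 5 points of power

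*Combined protocol and SAP*

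**What the plan says.** Section 3.2 defines a binary primary endpoint: "Spontaneous preterm delivery at less than 34 weeks gestation". Section 7.2 gives one general rule for such data: "Univariate comparisons of dichotomous data will be performed with Fishers exact test". It gives one criterion for significance: "The p values for all hypotheses will be two sided, and p values of less than 0.05 will be considered to be significant". For the size of the effect it says: "The risk of spontaneous preterm birth before 34 weeks will be quantified by use of the relative ratio and 95% confidence interval".

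The Study Summary describes the same quantity differently, "by use of the odds ratio and 95% CI".

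Neither place names the method for the interval. Section 7.2 also lists logistic regression and a Kaplan-Meier analysis, and does not label any analysis as primary. That Fisher's test supplies the primary p value is therefore read from the general rule for dichotomous data; the plan does not say so for this endpoint by name. Section 7.1 sizes the trial for 70% against 50%, 80% power and a 5% level, giving 93 per arm, and enrols 100 per arm.

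**The concern.** A test and an interval agree at the 5% line only if one is derived from the other. Fisher's test conditions on both margins of the 2x2 table, and its natural companion is a conditional interval for the odds ratio. The usual intervals for a relative risk (log-Wald or score) come from unconditional large-sample methods and are less conservative. Some tables will therefore give an interval that excludes 1 beside a p value that is not significant.

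Two things are at stake. The main table of the report could appear to contradict itself on the trial's one primary question, with no sentence in the plan to say how that is read. And the test that decides significance is more conservative than the one whose formula yields the sample size, so the planned numbers buy less power than section 7.1 states.

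**Working it through.** **Inputs.** Rates 70% and 50%, power 80%, 5% level, 93 and 100 per arm (7.1); two-sided testing and Fisher's test (7.2); 1:1 allocation (5.2). The log-Wald interval is an assumption, since no method is named.

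**1. The plan's own figure.** The uncorrected two-proportion formula with pooled variance under the null is

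n = [1.960·√(2·p̄·(1−p̄)) + 0.8416·√(p₁(1−p₁) + p₂(1−p₂))]² / (p₁−p₂)²

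With p̄ = 0.60: 1.960·√0.48 = 1.358 and 0.8416·√0.46 = 0.571. Their sum squared is 3.720, and 3.720/0.04 = 93.0. This reproduces 93 per arm. The formula belongs to the uncorrected Pearson (score) test, not to Fisher's.

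**2. One worked table.** Cerclage 56/100, control 70/100.
- RR = 0.56/0.70 = 0.80.
- SE(log RR) = √(1/56 − 1/100 + 1/70 − 1/100) = √0.01214 = 0.1102.
- 95% CI = 0.80·exp(±1.96·0.1102) = 0.645 to 0.993, which excludes 1.
- Pearson: z = 0.14/√(0.63·0.37·2/100) = 2.05, p = 0.040.
- Fisher: p = 0.057.
- Odds ratio = (56/44)/(70/30) = 0.55; its Wald upper limit is about 0.98, so that interval excludes 1 as well.

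**3. How wide the band is.** At 100 per arm, for control counts 61 to 80, each count except 75 has exactly one lower cerclage count at which the log-Wald interval excludes 1 and Fisher does not reject. Fisher's p in those tables runs from 0.0502 to 0.0649.

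**4. How often it happens.** Every 2x2 table was enumerated, classified by each procedure, and weighted by its binomial probability.

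| True rates | n per arm | Fisher p<0.05 | Log-Wald RR interval excludes 1 | Pearson p<0.05 | RR interval excludes 1, Fisher p≥0.05 |
|---|---|---|---|---|---|
| 70% v 50% | 93 | 75.1% | 79.1% | 79.9% | 4.0% |
| 70% v 50% | 100 | 79.2% | 83.0% | 83.2% | 3.8% |
| 70% v 70% | 93 | 3.4% | 4.9% | 5.1% | 1.5% |
| 70% v 70% | 100 | 3.5% | 4.8% | 5.1% | 1.3% |

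The reverse conflict (Fisher significant, interval including 1) had probability 0 to four decimals in every scenario run.

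**5. Does it depend on the interval assumed?** Little. At 70% against 50% the conflict with Fisher is 3.9% (100 per arm) and 4.3% (93 per arm) for a Wald odds-ratio interval, and 4.0% and 4.8% for a score interval.

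**6. What a matched pair does.** The score interval for a relative risk θ collects the values not rejected by

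z(θ) = (p̂_T − θ·p̂_C)/√[p̃_T(1−p̃_T)/n + θ²·p̃_C(1−p̃_C)/n]

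where the p̃ are the estimates constrained to p_T = θ·p_C. At θ = 1 this is Pearson's z, so the interval excludes 1 exactly when Pearson's p is below 0.05. Pearson's test beside a log-Wald interval is nearly matched: at 70% against 50% they disagree with probability 0.2% (100 per arm) or 0.9% (93 per arm).

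**7. Power.** With Fisher's test, 101 evaluable per arm give 79.9% and 102 give 80.6%.

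**The case against.** The strongest reply is that the plan has one decision rule, not two. Section 7.2 declares that "p values of less than 0.05 will be considered to be significant", and the interval only has the task of quantifying the risk. On that reading the table in step 2 has one answer: not significant. This stands. A reader might infer that the trial has two rival criteria and that the favourable one could be chosen once the data are seen. The documents do not support that, because nowhere do they let an interval excluding 1 establish efficacy. What remains is that the plan does not say in so many words how a conflicting pair is to be read.

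A reader might also infer an inflated false-positive rate. That too is unsupported: Fisher's actual size is about 3.5% at a 70% rate, and the conflict runs only in the conservative direction.

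The band is narrow, and both outputs in it describe the same borderline result. Larger probabilities can be produced, for example 5.6% at 70% against 56% with 100 per arm, but that scenario is not in the documents and lies close to the decision boundary.

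It is also fair to say that Fisher's p beside a relative risk is a permissible combination, and that the Study Summary's odds ratio could be paired with a conditional exact interval. That would make the report more coherent, but the power loss would remain. With event rates of 50% to 70% the odds ratio is also much further from 1 than the relative risk (0.55 against 0.80 in step 2).

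**Conclusion.** The point holds as a modest one. The primary test and interval are unmatched, the interval method is unnamed, and the two sections name different effect measures. The chance that the primary report contradicts itself is about 4% at the design rates and about 1.3% to 1.5% under a 70% null.

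The more tangible cost is power: Fisher gives up 4.8 points at 93 per arm (79.9% − 75.1%) and 4.0 points at 100 (83.2% − 79.2%). It thus falls short of 80% at the evaluable size, and marginally so even with no losses.

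This rests on three assumptions: Fisher's test is the source of the primary p value; the unnamed interval is log-Wald (Wald odds-ratio and score intervals give similar figures); and the unadjusted comparison is the primary one.

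**What to change.** In section 7.2, state that the primary conclusion rests on one matched pair: the relative risk with its score 95% interval (the Koopman form, which inverts the uncorrected Pearson test) and the uncorrected Pearson p value, two-sided at 5%. Keep Fisher's exact test for sparse outcomes. Amend the Study Summary to name the same effect measure.

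The plan commits all analyses to one named software package, and the documents do not show whether it produces a score interval. If it does not, use Pearson's test with a log-Wald interval for the relative risk and state that the p value governs. The small residual disagreement in step 6 then has a stated answer.

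The cost is a few sentences in two places, with no change to design or enrolment. The statistical price is that the actual two-sided size rises from about 3.5% to about 5.1% at a 70% rate. At a 50% rate with 100 per arm it rises from 4.0% to about 5.6%. If strict control at 5% is preferred, Fisher can stay as the governing test, provided that the plan says so, names the interval method, and either accepts the lower power or plans for about 102 evaluable women per arm.
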